Endpoints	
 
• All-cause in-hospital mortality
 
• Morbidity at defined post-diagnosis intervals and over 7 consecutive days 
 
- Mean total SOFA score (age <math>\geq 16</math>)
 
- PELOD score (age <math>< 16</math>)
 
- <math>\Delta</math>SOFA or dPELOD score for day-to-day comparisons
 
 
 
• Extent and severity of Purpura lesions
 
• Need for reconstructive surgery (amputations, skin grafts)
 
• Length of ICU stay (days)
 
• Length of hospital stay (days)
 
• Changes in hematological parameters 
 
- WBC count
 
- Thrombocyte count
 
- Hemoglobin
 
 
 
• Changes in coagulation parameters 
 
- Prothrombin time (PT)
 
- Activated partial thromboplastin time (aPTT)
 
- Fibrinogen
 
- D-dimers
 
- Thrombin-antithrombin complex (TATc)
 
- Protein C activity
 
- Antithrombin III activity
 
 
 
• Changes in inflammatory parameters 
 
- C-reactive protein (CRP)
 
- Procalcitonin (PCT)
 
- Interleukin 6 (IL-6)
 
 
 
• Changes in organ dysfunction parameters 
 
- Glucose
 
- Lactate
 
- Creatine kinase (CK)
 
 
 
• Duration of mechanical ventilation (days)
 
• Duration of renal replacement therapy (days)
 
• Vasopressor use (days/doses)
 
• Sepsis-inducing pathogen
 
• Adverse event related to PF treatment (reporting as per decision of the investigator) 
 
- Bleeding
 
- Thrombotic events
 
 
 

Inclusion criteria	
 
- Diagnosis of severe sepsis and Purpura fulminans
 
- Signed informed consent (according to local legal regulations)
 

Exclusion criteria	
 
- premature neonates (<math>< 36</math> gestational week)
 

Centers	Approx. 30 participating centers in Germany, Austria, Ireland, UK, Italy, Spain, Netherlands (selected centers)

Timetable	First patient in	Q3 2015
	Registry duration	3 years, with an option of prolongation
	Estimated enrolment	Approx. 50 patients/year
	Interim Analysis	Biannually

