**Flowchart**

Activity / Endpoint	Baseline 	Post-diagnosis period (days)					End of study at hospital discharge or in-hospital death after ICU discharge
		1	3	5	7	ICU discharge or death on ICU after day 7	
Confirm inclusion criteria	x						
Provision of informed consent 	x						
Demographic data collection (incl. ethnic origin)	x						
Risk factors (vaccination status, asplenia) and comorbidities	x						
Estimated time of SAPF onset (hours)	x						
Mortality prediction (APACHE II/SAPS II  or PRISM III  score)	x						
Morbidity assessment (SOFA  /PELOD  score)	x	x	x	x	x		
Laboratory parameters (hematology, coagulation, inflammation)	x	x	x	x	x		
Purpura lesion assessment (c.f. eCRF)	x	x	x	x	x		
Vasopressor use record	x	x	x	x	x	x	
Site, source and origin of infection (including viral)							x
Concomitant causal, supportive and adjunctive treatment (c.f. eCRF)		x	x	x	x	x	
Cumulative dose of blood products and anti-coagulant treatment		x	x	x	x	x	
Antimicrobials		x	x	x	x	x	
Days in ICU							x
Days on mechanical ventilation							x
ECMO and circulatory support systems		x	x	x	x	x	
Days/type on renal replacement therapy							x
Purpura-related surgery (fasciotomy, debridement, amputation)							x
In-hospital mortality assessment		x	x	x	x	x	x
Days in hospital							x
Adverse drug reactions							x

 admission at ICU; according to local regulations APACHE II/SAPS II and SOFA scores will be used in patients aged above 16 PRISM III and PELOD scores will be used in patients aged below 16

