### 8.3. Variables

The selection of the endpoint all-cause in-hospital mortality is justified, in view of the exceptional severity of the disease *per se* and considerable risk associated with the subsequent management of its late sequelae (e.g. reconstructive surgery). On a case-by-case basis, a comparison with the probability of a lethal outcome, as defined by the APACHE II/ SAPS II or PRISM III score, will be made.

Changes in morbidity (as assessed by the SOFA or PELOD indices) will be presented by the difference between scores measured at admission and after 1, 3, 5 and 7 days upon being diagnosed with SAPF ( $\Delta$ SOFA, dPELOD), as well as by the mean total score (SOFA, PELOD) recorded over the observation period of 7 days.

Records will also include description of imminent surgical interventions (during the SAPF treatment), as well as reconstructive measures (skin grafting, amputation).

The sepsis-inducing pathogen and the primarily affected organ will be identified by the results of microbiological examinations and in accordance with clinical manifestations.

Further endpoints comprise the length of stay in the ICU and the total duration of hospitalization (including time of post-SAPF therapy).

Changes in hematological, coagulation and inflammatory parameters will be monitored at selected intervals across the treatment and serve as biomarkers of treatment efficacy or surrogate endpoints, as follows:

- Thrombocyte counts
- Leukocyte counts
- Hemoglobin
- Prothrombin time (PT)
- Activated partial thromboplastin time (aPTT)
- Fibrinogen
- D dimers
- Thrombin-Antithrombin complex (TATc)
- Protein C activity
- Antithrombin III activity
- C-reactive protein (CRP)
- Procalcitonin (PCT)
- Interleukin 6 (IL-6)

Several of these parameters have been used in clinical studies and shown significant changes in the course of therapeutic interventions in sepsis and Purpura fulminans [Bernard et al., 2001; de Kleijn et al., 2003; Schellongowski et al., 2006; Shorr et al., 2008].

Laboratory indices of organ dysfunction are confined to measurements of

- Glucose
- Lactate
- Creatine kinase

Recording of adverse events related to the treatment of SAPF is left at the discretion of the local site investigator (c.f. comment in 9.9. *Limitations of research methods*); the emphasis is laid on

- bleeding incidents
- thrombotic events

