## 8.7. Data analysis

A binary logistic regression model will be fitted for the all-cause in hospital mortality to compare the efficacy of the different treatments (e.g. with or without Protein C supplementation). To adjust for confounders, causal pathogen, baseline Apache II (PRISM III) score, laboratory parameters, age, sex, co-medication etc. can be included as covariates in this model.

Consecutive changes in SOFA or PELOD scores ( $\Delta$ SOFA, dPELOD) at individual post-diagnosis intervals and their mean values calculated for the observation period of 7 days will be compared to the scores determined on admission (baseline). Changes in these organ failure indices will be examined by means of

- Paired samples T-test
- Linear model with morbidity score baseline adjustment and alternative co-variables (e.g. hematological, coagulation or inflammatory parameters)

Explorative analysis without correction and with a pre-set level of significance of 0.05 will be conducted as well.

All endpoints will be subjected to descriptive statistical analysis with determination of 95-percent confidence intervals. Between-group comparisons will be preceded by distribution analysis (Shapiro-Wilk Test of normality). Depending on the data distribution, *post hoc* processing will involve either parametric (one-way ANOVA, T test) or non-parametric (Kruskal-Wallis, Mann-Whitney U-test) approaches.

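### For laboratory endpoints, section 8.7 lets a normality test choose the between-group test and its estimand, and makes no efficient use of the measured baseline value

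*Combined protocol and SAP*

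**What the plan says.** Section 8.7 describes three kinds of analysis.

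- **Mortality:** "A binary logistic regression model will be fitted for the all-cause in hospital mortality to compare the efficacy of the different treatments". Pathogen, baseline severity score, laboratory values, age, sex and co-medication may enter as covariates.
- **SOFA and PELOD:** a paired t-test and a "Linear model with morbidity score baseline adjustment and alternative co-variables (e.g. hematological, coagulation or inflammatory parameters").
- **Between-group comparisons generally:** "Between-group comparisons will be preceded by distribution analysis (Shapiro-Wilk Test of normality"). Depending on the outcome, "processing will involve either parametric (one-way ANOVA, T test) or non-parametric (Kruskal-Wallis, Mann-Whitney U-test) approaches". The plan does not give the level of the pre-test, say whether it applies to each group or to residuals, or say whether the t-test assumes equal variances.

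The section adds: "Explorative analysis without correction and with a pre-set level of significance of 0.05 will be conducted as well".

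The laboratory endpoints are framed as changes, for example "Changes in inflammatory parameters" in the abstract and "Changes in hematological, coagulation and inflammatory parameters will be monitored at selected intervals across the treatment" in section 8.3. That section treats them as efficacy biomarkers or surrogates. The flowchart in section 8.2 schedules "Laboratory parameters (hematology, coagulation, inflammation") at baseline and on days 1, 3, 5 and 7. Glucose, lactate and creatine kinase are not named in that row, but the abstract lists them as changes too, which presupposes a baseline value.

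**The concern.** Section 8.1 puts particular weight on comparing outcomes with and without Protein C. For the laboratory parameters, the Shapiro-Wilk rule is the only method stated for that comparison. Three weaknesses follow.

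1. A t-test compares means; a Mann-Whitney test compares rank ordering. If the sample decides which is run, the quantity being estimated is not fixed in advance and may differ between parameters, days or biannual analyses.
2. A normality check says nothing about unequal variances. If the t-test is the pooled one, the rule gives no protection against them.
3. None of the four named tests takes a covariate. The baseline value enters at most through a change score, and baseline severity and other confounders do not enter at all. Under section 9 the physician chooses the treatment, so the groups cannot be assumed comparable.

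At stake are interpretability and precision in a registry whose section 8.5 concedes a limited size.

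**Working it through.** The documents state no effect size, SD, correlation, group ratio, power or error rate for these comparisons, so there is no figure to reproduce. Every result below is conditional on the inputs listed.

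**Inputs from the documents**
- Size: about 50 patients a year for 3 years (abstract), so 3 × 50 = 150. Section 8.5 allows 50 to 70 in year 1 and up to 100 a year later, so at most 250 to 270.
- Significance level 0.05, uncorrected (section 8.7).

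**Assumed inputs**
- Two-sided tests; Shapiro-Wilk at 0.05 in each group; pooled t-test if neither group rejects, otherwise Mann-Whitney.
- Power: 75 per group, log-normal marker with sigma 0.8, log shift 0.3, baseline correlation ρ of 0.3 or 0.6.
- Type I error: normal data, several splits and SD ratios.

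**Step 1: precision.** With post-value variance set to 1, a change score has variance 2(1−ρ) and a baseline-adjusted model has 1−ρ².

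| ρ | Change score | Adjusted | Adjusted / change |
|---|---|---|---|
| 0.3 | 1.40 | 0.91 | 0.65 |
| 0.5 | 1.00 | 0.75 | 0.75 |
| 0.7 | 0.60 | 0.51 | 0.85 |

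Adjustment is never less precise than either alternative. A change score is worse than ignoring baseline when ρ is below 0.5.

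**Step 2: power.** For the adjusted log-scale model, z = (0.3/0.8) × √(75/2) / √(1−ρ²).
- No adjustment: z = 0.375 × 6.124 = 2.296; power ≈ Φ(2.296 − 1.96) = 63%.
- ρ = 0.3: z = 2.296/0.954 = 2.407; power ≈ 67%.
- ρ = 0.6: z = 2.296/0.8 = 2.870; power ≈ 82% (normal approximation).

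Simulation gives:

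| ρ | Two-stage, post values | Two-stage, change scores | Adjusted, log scale |
|---|---|---|---|
| 0.3 | 61% | 46% | 67% |
| 0.6 | 60% | 69% | 80% |

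At ρ = 0.6, Mann-Whitney on post values without any pre-test also gives 61%, and an unadjusted log-scale Welch test 63%. Nearly all the gain over post values therefore comes from using the baseline, not from removing the pre-test.

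**Step 3: type I error** (6,000 runs per row, normal data).

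| Split | SDs | Two-stage | Pooled t alone | Welch |
|---|---|---|---|---|
| 30:120 | equal | 4.9% | 4.6% | 4.7% |
| 75:75 | ratio 2 | 5.0% | 4.6% | 4.6% |
| 50:100 | smaller group × 1.5 | 9.1% | 9.1% | 5.4% |
| 50:100 | smaller group × 2 | 11.2% | 11.2% | 4.6% |
| 30:120 | smaller group × 2 | 17.6% | 17.9% | 4.9% |
| 30:120 | larger group × 2 | 0.6% | 0.4% | 5.0% |

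At 20:80 with the smaller group twice as variable, the rule gives about 17%. In the reverse case it gives 0.4%, and with equal SDs about 5%. The two-stage rule tracks the pooled t-test, so the pooled variance is the cause. Keeping the pre-test but using Welch in the parametric branch gives 6.3% at 20:80.

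**Step 4: the estimand.** For log-normal data with equal means but different scale, Shapiro-Wilk rejects in about 100% of runs and the rank test then rejects in 43% to 62%, including 62% at 75:75. This is not a pure alpha error, because the distributions do differ. It shows that the two branches answer different questions.

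**The case against.** The strongest case on the other side is that this is a registry with exploratory secondary comparisons. Mortality has its own regression model. Section 8.5 accepts that group differences may be shown only for selected endpoints, and section 8.9 is cautious about inflammatory markers. All of this stands, and it limits the seriousness of the point. It does not explain why the choice of test should be left to the data.

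A reader might also infer stronger claims that the documents do not support.

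- **That the plan ignores baseline altogether.** It does not. SOFA and PELOD have a baseline-adjusted model, and a test on laboratory changes uses baseline, though inefficiently. The 60% on post values is therefore not the only comparator; the change-score figures belong beside it.
- **That the pre-test, or unequal group size, inflates type I error.** Neither does so alone. The inflation needs the pooled t-test and a smaller group that is more variable. Section 8.7 does not say which t-test is meant, and no group sizes or SDs are given.
- **That a skewed marker would probably pass as normal by day 7.** For the assumed marker, Shapiro-Wilk rejects in about 48% of draws at n = 10, 83% at n = 20 and 99% at n = 40. If half of 150 patients remained in an even split, about 37 per group, rejection would still be near-certain. Switching of tests is a risk only in much smaller subsets.
- **That every laboratory value needs a log scale.** Nothing in the documents shows skew for hemoglobin, prothrombin time or Protein C activity, for example.

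It is also fair to say that adjusting only for a marker's own baseline would leave confounding by treatment choice, which matters more here than lost precision.

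**Conclusion.** The point holds for the laboratory endpoints. Section 8.7 fixes neither the test nor the estimand, offers no stated safeguard against unequal variances, and makes poor use of the baseline values.

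Under the stated assumptions, baseline adjustment gains 6 points of power over post values at ρ = 0.3 (67 − 61) and 20 at ρ = 0.6 (80 − 60). Over change scores it gains 21 (67 − 46) and 11 (80 − 69). These gains depend on the assumed correlation, sigma, shift and even split. The type I error problem is conditional: about 17% in one adverse configuration, nominal with equal SDs, and conservative in the reverse configuration.

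The change should be made, but the point does not undermine the mortality analysis or the SOFA/PELOD model.

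**What to change.** In section 8.7, delete the Shapiro-Wilk step and state one analysis per endpoint in advance.

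- **Laboratory parameters:** a linear model with Protein C use, the parameter's own baseline value and robust standard errors. Include the same confounder covariates already listed for the mortality model, as a fixed list, because treatment is physician-chosen.
- **Scale:** logarithmic for markers named in advance as skewed (for example CRP, PCT, IL-6, D-dimers and CK); the measured scale otherwise.
- **Variables without a baseline:** Mann-Whitney only for those named in advance.
- **Flowchart:** confirm that the laboratory row covers glucose, lactate and creatine kinase at baseline.

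The model uses values the plan already schedules or presupposes, and extends the plan's own SOFA/PELOD approach. The cost is a few rewritten sentences, slightly more analysis work, and effects reported as ratios for the log-scale markers. Robust or unequal-variance methods are not exact either: in the same simulations Welch gave 6.5% to 6.8% for identically distributed log-normal data at 30:120. This is one more reason to settle the scale for skewed markers beforehand.

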## **8. Research methods**

### **8.1. Study design**

The registry comprises prospective, open-label data collection on the current state of incidence and management of SAPF, regardless of the etiopathogenic background. Using appropriate statistical techniques, specific emphasis will be laid on the comparison of outcomes in therapeutic approaches including or avoiding supplementation with Protein C formulations.

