### **8.2. Setting**

The registry will include comprehensive records on diagnosis, morbidity and management of SAPF, supplied in the form of eCRFs by the participating centers over a period of three years.

The provision of informed consent by the patient or patient's legal guardian will be required for inclusion in accordance with local legal regulations.

The causal SAPF-inducing pathogen will be identified by microbiological examination.

The presence of Protein C deficiency and its contribution to the clinical manifestations of SAPF will be examined upon enrolment by determinations of Protein C concentration and activity, and subsequently documented in the eCRF. Changes in Protein C levels resulting from supplementation will be monitored as well.

The registry will also compare data on the efficacy of therapeutic approaches including or omitting Protein C supplementation.

A further aspect of specific interest is the stratification of outcomes by demographic (e.g. age, sex) and clinical criteria (e.g. morbidity at admission, causal pathogen), in order to identify subgroups of patients with above-average or marginal responsiveness to Protein C supplementation.

The contribution of supportive measures (e.g. assisted ventilation, renal replacement therapy, fluid resuscitation) and co-medication (e.g. vasopressors, corticosteroids, heparin etc.) will be evaluated as well.

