## 9. Protection of human subjects

The Registry protocol is subject to approval by the IRB of the Friedrich Schiller University, Jena, which will serve as the supervisory ethic institution in charge. Approval of the Registry protocol by the responsible regional or national authorities will be sought after by participating centers which are outside of the jurisdiction of the IRB in charge.

Eligibility for an individual treatment modality will be defined by the responsible physician by fulfillment of the criterion "manifest clinical signs of sepsis-associated *Purpura fulminans*". The probability of inclusion into the Registry will not influence the physician's decision on the use of a selected medication.

An informed consent, signed by the patient or his/her legal representative, also comprising collection and use of medical data, will be sought for before enrolment into the Registry. However, in view of the rarity of the disease and the high mortality, usage of deviant regional and national regulations will be considered where appropriate and legally acceptable.

The protection of participant's privacy will be warranted by **a)** pseudonymization of patient personal data at the participating center for the duration of the clinical observation period, **b)** data transmission using a secure password-protected login and **c)** ultimate anonymization of the collected information upon verification of data consistency and plausibility. The pseudonymous ID list will

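### Protein C is given at the physician's choice, yet Section 8.7 makes confounder adjustment optional for mortality, states no treatment term for SOFA/PELOD, and names only unadjusted tests for durations and laboratory changes

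*Combined protocol and SAP*

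**What the plan says.** - **Treatment assignment.** Section 9: "Eligibility for an individual treatment modality will be defined by the responsible physician". Section 8.1 describes the design: "The registry comprises prospective, open-label data collection on the current state of incidence and management of SAPF". Nothing balances the groups.
- **Comparative aim.** Section 8.1: "Using appropriate statistical techniques, specific emphasis will be laid on the comparison of outcomes in therapeutic approaches including or avoiding supplementation with Protein C formulations". Section 8.2: "The registry will also compare data on the efficacy of therapeutic approaches including or omitting Protein C supplementation". Section 7 lists a comparative assessment of strategies with and without Protein C, and recommendations for its routine use, among the registry's aims.
- **Mortality (Section 8.7).** "A binary logistic regression model will be fitted for the all-cause in hospital mortality to compare the efficacy of the different treatments". The candidate confounders are causal pathogen, baseline APACHE II (PRISM III) and then "laboratory parameters, age, sex, co-medication etc. can be included as covariates in this model".
- **SOFA/PELOD (Section 8.7).** A paired t-test and a linear model with baseline-score adjustment and alternative co-variables, for which laboratory markers are the examples. The stated contrast is with each patient's admission score. No Protein C term is given.
- **Other endpoints (Section 8.7).** Descriptive statistics with 95% confidence intervals. Between-group comparisons follow a Shapiro-Wilk test and use "parametric (one-way ANOVA, T test) or non-parametric (Kruskal-Wallis, Mann-Whitney U-test) approaches". No covariates are mentioned. These tests do not suit a yes/no endpoint such as need for surgery, and no other method is given for it.

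**The concern.** When physicians choose the treatment, sicker patients may be more or less likely to receive Protein C. Severity also drives length of stay, organ support and laboratory course. A two-group t-test or rank test then estimates the Protein C effect plus the severity difference and cannot separate them. The choice between t-test and rank test on the Shapiro-Wilk result does nothing about this.

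For mortality the gap is one of specification. A model with no covariates, or with covariates picked after seeing the results, would comply with Section 8.7 as written.

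The stakes are practical. Section 11 says the Advisory Committee will compile and update SAPF therapy recommendations from the biannual evaluations, so a confounded contrast could reach clinical guidance.

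**Working it through.** The plan has no power or sample-size calculation for the Protein C comparison, so there is no figure to reproduce. The check has two parts.

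**1. What Section 8.7 specifies for a Protein C comparison**

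| Endpoint | Between-group method named | Adjustment |
|---|---|---|
| In-hospital mortality | Logistic regression | Permitted, open-ended list |
| SOFA/PELOD | Linear model, no treatment term stated | Baseline score; other covariates not fixed |
| Length of stay, ventilation days, renal replacement days | t/ANOVA or rank test | None |
| Laboratory changes | t/ANOVA or rank test | None |
| Surgery (yes/no) | None suited to it | None |

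Confounding is mentioned elsewhere, but without a method for this comparison. Section 8.4 says the influence of confounders will be inferred from eCRF entries. Section 8.2 stratifies outcomes in order to find responder subgroups. Section 8.9 carries the co-medication caveat into eCRF design.

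**2. How large the distortion could be**

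Input from the documents: about 50 patients a year for 3 years (Section 4), so N = 150. Assumed inputs: a 1:1 split (75 per group), no true effect, two-sided 0.05, severity standardised to SD 1, odds of Protein C of 1.5 or 2 per SD of severity, and severity-endpoint correlation r of 0.3 or 0.5.

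With log-odds b per SD, the severity gap between groups is 4 × b × E[p(1−p)], where p is the probability of receiving Protein C:

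- odds 1.5: 4 × 0.4055 × 0.2405 = 0.390 SD
- odds 2: 4 × 0.6931 × 0.2254 = 0.625 SD

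The shift of the test statistic is δ = gap × r / √(2/75) = gap × r / 0.1633. The rejection rate is 1 − Φ(1.96 − δ) + Φ(−1.96 − δ).

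| Odds per SD | r | δ | Rejection, formula | Rejection, simulation |
|---|---|---|---|---|
| 1.5 | 0.3 | 0.72 | 11% | 11–12% |
| 1.5 | 0.5 | 1.19 | 22% | 22% |
| 2 | 0.3 | 1.15 | 21% | 19–20% |
| 2 | 0.5 | 1.91 | 48% | 48–49% |

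The Mann-Whitney test rejects in 11–21% (odds 1.5) and 20–46% (odds 2), so the rank branch gives no protection. A linear model with severity as covariate rejects in 4–5%.

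A second set of assumptions fixes the gap directly, with r = 0.5. For a gap of 0.5 SD, δ = 0.5 × 0.5 / 0.1633 = 1.53, and the rate is 33%. Simulated t-test rates at gaps of 0.3, 0.5 and 0.8 SD are 15%, 33% and 68%, against about 5% adjusted. By the formula, gaps of 0.2 to 0.8 SD with r from 0.3 to 0.7 give 7% to 93%.

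For mortality, suppose the model were fitted without covariates and severity carried assumed log-odds of 1.2 per SD. With odds of Protein C of 1.5, the death risks would be 54.57% and 45.43%, an odds ratio of (0.5457/0.4543)² = 1.44 where the truth is 1. With odds of 2 they would be 57.37% and 42.63%, an odds ratio of (0.5737/0.4263)² = 1.81.

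**The case against.** **The plan does adjust.** This is partly right. A reader might infer that adjustment is missing for everything except mortality, or that mortality too is left to t-tests and rank tests. The documents support neither. Section 8.7 lists a baseline-adjusted linear model for SOFA/PELOD, and for mortality a logistic model with a sentence whose stated purpose is confounder adjustment. What remains is that the mortality covariates are neither required nor fixed, and that the SOFA/PELOD model is not set up as a Protein C comparison.

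**The unadjusted tests are secondary.** They stand in a paragraph that opens with descriptive analysis and does not define the groups, and Section 8.5 warns that treatment differences may be demonstrable only for selected endpoints. That softens the point. But Sections 7, 8.1 and 8.2 claim a comparison of efficacy, and for durations and laboratory changes these are the only between-group methods on offer.

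**The size is assumed.** This stands. The documents give no treatment-severity association and no severity-endpoint correlation. The 5% after adjustment is also built in, because the calculation makes one perfectly measured score the only confounder.

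**Adjustment can go wrong with so few patients.** This also stands, and it limits the remedy. About 150 patients in about 30 centres is 150/30 = 5 per centre, too few for fixed centre terms. The logarithm of zero ventilation or renal replacement days is undefined, and with mortality above 50% (Section 6) many durations are cut short by death.

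**Conclusion.** The point holds as a gap in Section 8.7. Treatment is physician-selected and its comparative efficacy is an aim, yet adjustment is optional for mortality, the SOFA/PELOD model has no stated Protein C term, durations and laboratory changes have only unadjusted tests, and surgery has no named method.

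Under the assumed selection model the false-positive rate at N = 150 is about 11% to 48% unadjusted, against about 5% with severity adjustment. These figures show that modest selection by severity is enough to matter. They do not predict what this registry will find.

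Two stronger readings should be avoided. The mortality odds ratios of 1.44 and 1.81 belong to an uncovaried model that the plan allows but does not prescribe, so they are not the plan's expected result. And surgery is not assigned a t-test or rank test; its analysis is simply unspecified.

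**What to change.** In Section 8.7:

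1. **Mortality.** Replace "can be included as covariates in this model" with a requirement to include a short, fixed set of baseline covariates: severity score on the age-appropriate scale, adult/child, sex and baseline platelets, with causal pathogen group if numbers allow. With Protein C that is five terms before pathogen. At 50% mortality there are about 75 deaths and 75 survivors, or 75/5 = 15 per term. Co-medication is better left out of the required set, because the flowchart records it only from day 1 and it may follow from treatment.
2. **SOFA/PELOD.** State a Protein C term in the linear model and use the same set.
3. **Other Protein C comparisons.** Use the same set in regression: logistic for surgery; linear for laboratory change, with the parameter's own baseline value added; and for durations a method that accepts zeros and deaths, such as covariate-adjusted ordinal regression with death ranked worst.
4. **Centre.** Do not use fixed centre terms. Use a random centre effect or cluster-robust errors as a sensitivity analysis.
5. **Unadjusted tests.** Keep the t, ANOVA and rank tests, labelled as descriptive only.

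The flowchart already collects severity scores, demographics and hematology at baseline, and the source of infection by the end of study. Section 9 retains the centre of origin. The cost is a revised section, a little more analysis work and somewhat wider intervals. Unmeasured confounding remains, and the report should say so.
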